7.4 PROTOCOL VIOLATIONS

All protocol violations will be summarized in the ITT population, including the frequency and percent of subjects with each violation type. Prior to database lock, all protocol violations will be reviewed and subjects who had major violations will be noted and excluded from the per-protocol population.

7.5 MULTIPLE COMPARISONS AND MULTIPLICITY

For the trial to be considered a success, both co-primary outcomes, the ODI and the VAS, must be statistically significant at an overall two-sided α -level of 0.05. Additionally, for each primary outcome, if the Kruskal-Wallis test is significant, pairwise comparisons will be analyzed using the Dwass, Steel, Critchlow-Fligner method, which controls the overall family-wise error rate.

No adjustments for multiple testing will occur for secondary endpoints, as the intention of these analyses is exploratory in nature.

8 DEMOGRAPHICS AND OTHER BASELINE CHARACTERISTICS

8.1 **DEMOGRAPHICS**

Baseline demographics and subject characteristics will be summarized in the ITT and mITT populations including, but not limited to, age, gender, race, ethnicity, smoking history, history of endocrine or metabolic disorders, level of treatment (1 vs. 2), and number of years experiencing back pain.

8.2 BASELINE NEUROLOGICAL EXAM

Baseline neurological exam will be presented in the mITT population. Motor function, reflex exam, and sensory exam will be summarized by the left and right side.

8.3 BASELINE VITAL SIGNS

Baseline vital signs will be summarized in the mITT population including height, weight, body mass index, blood pressure, pulse rate, and temperature.

8.4 BASELINE PHYSICAL EXAM

Baseline physical exam will be summarized in the mITT population by frequency and percent of subjects in each category that are categorized as normal or abnormal. An additional listing will be provided for any abnormal physical exam findings.

8.5 BASELINE LABS

Baseline hematology, clinical chemistry and coagulation labs will be summarized in the mITT population.

9 EFFICACY ANALYSES

The co-primary efficacy variables will be analyzed in the mITT population (primary) and repeated in the PP population (sensitivity). The secondary variables will be analyzed in the mITT and PP populations.

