6.8 Treatment compliance

A lack of compliance during the Screening Phase will result in an exclusion from the Active Phase of the study. Once treatment occurs, a subject can only be excluded from the study due to the following:

- 1. Withdrawal of consent
- 2. Lost- to follow-up
- 3. Death
- 4. Subject undergoes subsequent surgery on the treated disc
- 5. Investigator withdrawal due to subject's study compliance

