6.2 MODIFIED INTENT TO TREAT POPULATION (MITT)

The modified intent-to-treat population (mITT) includes all ITT subjects who underwent treatment and had at least one valid post-treatment assessment of the ODI and VASPI. This mITT population is the primary analysis population for efficacy analyses. Subjects are analyzed under the treatment to which they were randomized.

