6.4 SAFETY POPULATION

The safety population includes all ITT subjects who underwent treatment. The safety population is the primary population for analyses of adverse events. Subjects are analyzed according to the treatment which they received, regardless of initial randomization.

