9.2 SECONDARY ENDPOINTS

All secondary variables will be analyzed in an exploratory way, with no adjustment for multiple testing. The secondary endpoints include:

- Improvement in ODI and VASPI at 6 months
- Improvement in ODI, SF-36, and VASPI at 6 and 12 months after treatment
- MRI measurements at 6 and 12 months after treatment
- Adverse Event (AE)/ Serious Adverse Events (SAE) rates after treatment
- Hospitalization rate at 12 months after treatment
- Re-operation rate at 12 months after treatment
- Resource utilization following treatment at 6 and 12 months after treatment
- Changes in laboratory tests

Improvement in ODI, VASPI, and SF-36 will be analyzed similar to the primary endpoint, using the Kruskal-Wallis test to test for an overall difference between the three treatment groups. If the overall test is significant, the Dwass, Steel, Critchlow-Fligner Method will be used to asses all pairwise comparisons.

Adverse event rates, serious adverse events rates, hospitalization rates, and re-operation rate will be summarized by treatment group and compared using the chi-square test of independence or Fisher's exact test, as appropriate.

MRI data will be summarized by treatment group as mean at each timepoint, and mean change from baseline. Analyses will be done focusing on the level treated, but additional analyses will be completed which examine all five levels to see if there are adjacent level effects. Group comparisons will be made using the Krusal-Wallis test. If the overall test is significant, the Dwass, Steel, Critchlow-Fligner Method will be used to assess the pairwise comparisons.

Resource utilization and changes in laboratory tests will be summarized by treatment group.

10 Adverse Events

All adverse events will be coded using the standardized Medical Dictionary for Regulatory Activities (MedDRA) central coding dictionary, version 22.1 or greater.

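### Hospitalisation and re-operation rates are assigned only to mITT and PP, which can drop early failures; for AE/SAE rates the same rule conflicts with SAP 6.4

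*SAP*

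**What the plan says.** SAP section 9 sets one rule for every secondary variable: "The secondary variables will be analyzed in the mITT and PP populations". It makes no exception.

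SAP 9.2 then lists, as secondary endpoints, "Adverse Event (AE)/ Serious Adverse Events (SAE) rates after treatment", "Hospitalization rate at 12 months after treatment" and "Re-operation rate at 12 months after treatment". These rates are to be summarised by treatment group and "compared using the chi-square test of independence or Fisher's exact test, as appropriate". Section 9.2 names no population of its own, and neither does section 10, which describes the AE tables.

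SAP 6.2 limits mITT to treated subjects who "had at least one valid post-treatment assessment of the ODI and VASPI", grouped as randomised. PP (SAP 6.3) is a subset of mITT without major protocol violations. SAP 6.4 defines a safety population of all treated ITT subjects, with no questionnaire condition and grouped by treatment received, and adds: "The safety population is the primary population for analyses of adverse events".

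Protocol 6.8 gives the permitted reasons for excluding a subject after treatment. One is: "Subject undergoes subsequent surgery on the treated disc". Protocol 6.10 asks for every effort at a Termination Visit with the Month 12 procedures when a subject leaves early.

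**The concern.** Hospitalisation and re-operation are harm and failure outcomes, but their denominator is an efficacy population defined by a returned questionnaire. Whether a subject enters the denominator can then depend on the event being counted: someone re-operated or withdrawn before completing an ODI and VASPI may be missing from both numerator and denominator. The opportunity for such loss is not the same in all arms, because the questionnaire schedule differs. At stake are the level of the reported rates and the fairness of the between-group comparison planned for them.

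For AE/SAE rates the difficulty is of another kind. Two sections give different populations, and the reporting statistician could follow either.

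**Working it through.** **Which population governs which rate**

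| Rate | SAP 9 with 9.2 | SAP 6.4 | Result |
|---|---|---|---|
| AE, SAE | mITT and PP | safety population primary | conflict |
| Hospitalisation | mITT and PP | not named | mITT/PP only |
| Re-operation | mITT and PP | not named | mITT/PP only |

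Section 6.4 speaks of adverse events. It cannot be assumed to cover re-operation, because Protocol 8.5 has treatment failure, meaning the need for a follow-up operation, documented separately from AEs.

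**When the first post-treatment ODI and VASPI are due** (Protocol 7.1.3 to 7.1.5 and Appendix A)

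- Month 1: the first 24 randomised only, with at least 4 per group.
- Month 3: conservative care only.
- Month 6 (± 30 days): all subjects.

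Planned arm sizes (SAP section 4) are 140 allograft, 40 placebo and 40 conservative care, so 140 + 40 = 180 subjects are injected. Among the first 24, the number injected is at least 4 + 4 = 8 and at most 24 − 4 = 20. Injected subjects with no scheduled questionnaire before Month 6 therefore number between 180 − 20 = 160 and 180 − 8 = 172. For conservative care the first questionnaire falls at 3 months at the latest, so the period in which an early failure can be lost is about twice as long in the injected arms.

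**Effect on a rate**

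Let n be treated subjects, e those with an event, and d those with an event who never provide a valid post-treatment ODI and VASPI.

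- All treated: e/n
- mITT: (e − d)/(n − d)

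The documents state no event rate, so e and d are assumptions. For the allograft arm, n = 140:

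| e | All treated | d | mITT |
|---|---|---|---|
| 14 | 14/140 = 10.0% | 0 | 14/140 = 10.0% |
| 14 | 10.0% | 4 | 10/136 = 7.4% |
| 14 | 10.0% | 7 | 7/133 = 5.3% |
| 7 | 7/140 = 5.0% | 0 | 7/140 = 5.0% |
| 7 | 5.0% | 2 | 5/138 = 3.6% |
| 7 | 5.0% | 4 | 3/136 = 2.2% |

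To show the imbalance, suppose conservative care has the same underlying rate, 4/40 = 10.0%, and loses no one because of its 3-month questionnaire. With 7 lost in the allograft arm, the comparison would read 5.3% against 10.0% although the true rates are equal.

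The formula assumes that only subjects with events are lost. Event-free subjects who leave without a questionnaire shrink the denominator and partly offset the bias.

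**The case against.** The case against has real force on four points.

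1. *AE/SAE rates already have a population.* A reader might infer that AE and SAE rates are planned in mITT alone. The documents do not support that: SAP 6.4 is specific to adverse events and calls the safety population primary, whereas the section 9 sentence is general and sits under an efficacy heading. This stands. For AE/SAE rates the fault is an unreconciled conflict. The mITT/PP entry in the section 13 table of changes adds nothing, because that table is a summary of changes and is not evidence of an error.

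2. *Early failures remain visible.* SAP 10.1 to 10.5 list all AEs, SAEs, AEs leading to withdrawal, and deaths, and SAP 7.2 tabulates withdrawals by reason in ITT. Inpatient hospitalisation is itself an SAE criterion (Protocol 14.2). This stands too. It would be wrong to say that harm disappears from the report; the understatement concerns the separate hospitalisation and re-operation rates and their tests.

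3. *Loss is not automatic.* Protocol 6.8 permits exclusion after surgery on the treated disc but does not require it. The Termination Visit includes ODI and VASPI, physicians may recall subjects at any time, and one valid assessment of both scores keeps a subject in mITT. So loss can happen but need not. It does not remove the problem, because the Termination Visit is best effort and an unscheduled visit need not yield questionnaires.

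4. *The endpoints are exploratory.* They are unadjusted and do not decide trial success. That limits the consequence, but they remain planned between-group comparisons of harm and failure.

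**Conclusion.** The point holds for hospitalisation and re-operation rates. Their only stated population is conditional on a post-treatment questionnaire that 160 to 172 of 180 injected subjects are not scheduled to give before Month 6. This is a stated rule that can bias a result downward, and unequally between arms. For AE/SAE rates it holds only as a contradiction between SAP 9/9.2 and SAP 6.4.

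The size is unknown. With an assumed 10.0% re-operation rate in 140 allograft subjects, mITT would show anything from 10.0% (none lost) through 7.4% (4 lost) to 5.3% (7 lost). A reader might take from the last figure that the true rate is halved. That depends entirely on assuming 14 events, 7 of them without a questionnaire; if every Termination Visit is completed, the bias is zero. The counts use planned arm sizes and the range of injected subjects possible among the first 24 randomised.

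**What to change.** In SAP section 9, exempt AE, SAE, hospitalisation and re-operation rates from the mITT/PP sentence. Leave it in force for the other secondary variables, including resource utilisation and laboratory changes, so that none of them loses its population. Then add two statements:

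- AE and SAE rates use the safety population, as in section 6.4.
- Hospitalisation and re-operation rates use all treated subjects with no questionnaire condition, compared by randomised arm, with an as-treated display alongside.

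The second statement needs both groupings. Pointing these rates to the safety population alone would repair the denominator but group subjects by treatment received, and conservative-care subjects may cross over to allograft (Protocol 7.1.4). Those who do are a selected group, so the as-treated display does not preserve the randomised comparison.

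The cost is a few SAP sentences and one extra table, with no new data collection. Reported rates may be slightly less favourable.

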9.1 CO-PRIMARY EFFICACY ENDPOINTS

The co-primary endpoints are the change in ODI and VASPI at 12 months after treatment.

The hypothesis for the ODI is as follows:

H₀: $\tilde{x}_1 = \tilde{x}_2 = \tilde{x}_3$ H_a: at least one median is not equal

Where \tilde{x}_1 is the median pre-post difference in the active allograft group, \tilde{x}_2 is the median pre-post difference in the placebo group and \tilde{x}_3 is the median pre-post difference in the conservative care group.

The null hypothesis (H_0) for this endpoint states that there is no difference in change in ODI at 12 months between the three treatment groups (1) Active Allograft, (2) Placebo, and (3) Conservative Care. The alternative hypothesis (H_a) is that there is a difference in change in ODI at 12 months between the three treatment groups.

The hypothesis for the VASPI is as follows:

 $\begin{array}{l} H_0: \ {\tilde x}_1 = {\tilde x}_2 = {\tilde x}_3 \\ H_a: \ at \ least \ one \ median \ is \ not \ equal \end{array}$

Where \tilde{x}_1 is the median pre-post difference in the active allograft group, \tilde{x}_2 is the median pre-post difference in the placebo group and \tilde{x}_3 is the median pre-post difference in the conservative care group.

The null hypothesis (H₀) for this endpoint states that there is no difference in change in VASPI at 12 months between the three treatment groups (1) Active Allograft, (2) Placebo, and (3) Conservative Care. The alternative hypothesis (H_a) is that there is a difference in change in VASPI at 12 months between the three treatment groups.

For both the ODI and the VASPI, the pre-post difference of the groups will be compared using the Kruskal-Wallis test at a two-sided α -level of 0.05. If the result for either test is significant, then the Dwass, Steel, Critchlow-Fligner Method will be used to assess all pairwise comparisons for that endpoint.

Both the ODI and the VASPI need to be statistically significant (p<0.05) for the trial to be a success.

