	to the conservative care arm will also be evaluated at 2 months, during which they					
	to the conservative care and will also be evaluated at 3 months, during which they are aligible to reacive visible allograft					
	The first 24 subjects randomized (at least 4 in each treatment group) will have an					
	additional study visit at 1 month after treatment. All data from the 1-month study					
	visit will be reviewed by the Steering Committee to confirm enrollment may					
	continue.					
ENDPOINTS	The study's co-primary endpoints are:					
	• Improvement in the ODI at 12 months after treatment					
	 Improvement in the VASPI at 12 months after treatment 					
	· Improvement in the VIISFF at 12 months after freatment					
	The study's secondary and points are:					
	In survey a secondary enupoints are.					
	• Improvement in the ODI and VASPI at 6 months after treatment					
	• Improvement in SF-36 at 6 and 12 months after treatment					
	• MRI measurements at 6 and 12 months after treatment					
	• Adverse Event (AE)/ Serious Adverse Events (SAE) rates after treatment					
	Hospitalization rate at 12 months after treatment					
	• Re-operation rate at 12 months after treatment					
	• Resource utilization following treatment at 6 and 12 months after treatment					

INTERIM	For safety and efficacy reasons, interim analyses are planned to be performed after						
ANALYSES	the first 24 subjects have completed the Month 1 assessment of the Active Phase.						
	This analysis will be performed in a descriptive manner only and no un-blinding						
	will occur unless a safety signal is evident. A Steering Committee will be conve						
	to review the results of the interim analysis. A similar review will occur when the						
	complete the Month 6 assessment of the Active Phase, where primary endpoints of						
	pain and ODI, and randomized MRI will be available for analysis.						
FINAL ANALYSES	All final analyses identified in this SAP will be completed after the last subject has						
	completed the 12-month follow-up visit.						
	The co-primary endpoints will be tested using the Kruskal-Wallis test to compare						
across the three treatment groups at a two-sided α =0.05 level. If the overal							
significant, the Dwass, Steel, Critchlow-Fligner method will be use							
	pairwise comparisons, while controlling for the overall familywise error level.						
	Both of the co-primary endpoints need to meet statistical significance for the						

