4 SAMPLE SIZE

The primary criteria will be analyzed using Wilcoxon rank-sum-test. Based on Fairbanks, 2000¹, Hudson-Cook, 1989² and Fritz, 2001³ a common standard deviation of $\sigma = 15.5$ score points can be assumed.

Fritz, 2001, calculated a Minimum Clinically Important Difference of 6 score points. Reliability is reported in the literature in the range of 0.75 - 0.91. Worst case, using the standard deviation above results in a measurement error of 7.75 score points. Thus, we assume a clinically relevant difference of 9 score points. Under this assumption, the probability p (x < y) = 0.341 (x, y observations in the groups, respectively). A sample size of 40 in each group will have 80 % power to detect with a probability of 0.341 that an observation in one group is less than an observation in the other group using Wilcoxon rank-sum-test with a 0.05 two sided significance level (calculations were done using nquery 4.0).

Approximately 220 subjects randomized to viable allograft or placebo or control in 3.5:1:1 ratio:

Active Allograft = 140 Placebo = 40 Conservative Care = 40

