13 CHANGES IN THE PLANNED ANALYSIS

Section	Description	Justification
3.2.1 Co-primary	The primary endpoint is now a	The protocol inconsistently stated what the
endpoints	co-primary endpoint of the ODI	primary endpoint would be. It stated the ODI and
	and VASPI at 12 months.	VASPI at 6 and 12 months, but the primary
		analyses and powering was for the ODI at 12
		decided it would be a constructed of the way
		both endpoints would need to be met for the trial
		to be considered a success
3.2.2 Secondary	The ODI and VASPI at 12	The protocol repeated the primary endpoints in
endpoints	months was removed as a	the secondary endpoint section. The primary
-	secondary endpoint.	endpoints were removed from the secondary
		endpoint section.
6 Analysis	The mITT population will be the	The protocol summary stated the main analysis
Populations	primary analysis population for	would occur in the mITT population. The body
	efficacy and safety.	of the protocol stated analyses would occur in the
		written it was decided the mITT population
		would be used for the primary analyses and
		endpoints would also be run in the PP
		population.
7.3 Methods for	The primary analysis will be	The protocol summary did not indicate LOCF,
Withdrawals,	completed using available data.	but the body of the protocol noted the use of
Missing Data, and	A sensitivity analysis will be	LOCF. At the time this SAP was written it was
Outliers	performed using LOCF.	decided the primary analysis would occur in
		those with available data, and LOCF would be
		nopulation
9.1 Primary Efficacy	The primary efficacy analysis	The Kruskal-Wallis test is being used in place of
Endpoints	will be in the ODI and the	the Wilcoxon Rank Sum test as it is the
-	VASPI at 12 months. The	appropriate test for a three-group comparison,
	Kruskal-Wallis test will be used	where the Wilcoxon Rank Sum test is the
	in place of the Wilcoxon Rank	equivalent test for a two-group comparison. The
	Sum test. If the result is	addition of the Dwass, Steel, Critchlow-Fligner
	Critchlow Eligner Method will	evaluate which comparisons are significantly
	be used to assess all pairwise	different. The originally proposed responder
	comparisons. A responder	analysis was removed since it had the potential
	analysis that was initially	for results to be clinically incompatible due to
	described in the protocol was	the use of the Bonferroni-Holm procedure (e.g. a
	removed.	difference of 1 could be significant, but a

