		difference of a higher value may not be).
3.2.2 Secondary	X-ray data was removed from	X-ray data was listed with the MRI data in the
Endpoints and 9.2 Efficiency Endpoints	the secondary endpoints.	protocol. A-ray and MIKI data was collected, but
Encacy Enupoints		interpretation of the MRI data by the core lab
		Therefore, there is no x-ray data to analyze

14 References

				FORM			
		BBA			{T #:	FM - 32	
į				REVISION:		2.0	
QS - Study Spe	cific Document Revie	w & Appro	oval Form	CC #:	264	PAGE 1	OF 2
Sponsor: Vive	ex Biologics, Inc		Project Title	VAST	-001-017		
Document Type:	Statistical Analysis	Plan (SAP)	·······	Docum	ient Versi	on: A	
Text and Table Va	lidation Required?	Yes 🛛	🛛 No				
If Yes, Performed by:		Signature:			Date:		
Document Owner:	[name]	Signature:	[name]	Date:	30JAN202	20
Functional Role	Name		Date		Signatu	re	N/A
BBA President							
BBA Project Manager	[name]	30.JA	N 2020	[name]	
BBA Data Management Lead							
BBA SAS Programmer Lead	[name]	30JAN	2020	[name]	
BBA Stats Lead	[name]	30JAN	2020	[name]	
BBA Clinical Lead							\boxtimes
BBA Regulatory Lead							\boxtimes

This document is the property of Boston Biomedical Associates, LLC, and may not be reproduced, distributed, disclosed or used in any manner or for any purpose without the express written consent of Boston Biomedical Associates.

	FORM			
		ENT #:	FM - 32	
	REVISION:		2.0	
QS - Study Specific Document Review & Approval Form	CC #:	264	PAGE 2 OF 2	

Functional Role	Name	Date	Signature	N/A
BBA CEC Lead				\boxtimes
BBA DMC Lead				\boxtimes
BBA Medical Lead				\boxtimes
Sponsor Representative	[name]	01/30/20	[name]	
<other></other>				X

Comments:

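### The success rule needs only a non-directional three-group difference on each endpoint, so the trial can succeed when allograft does no better than saline

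*SAP*

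**What the plan says.** SAP 9.1 sets the same hypotheses for ODI and VASPI change at 12 months: three equal medians against the alternative that "at least one median is not equal". Each endpoint is tested by Kruskal-Wallis at two-sided 0.05. The success rule follows: "Both the ODI and the VASPI need to be statistically significant (p<0.05) for the trial to be a success". SAP 7.5 repeats it ("For the trial to be considered a success, both co-primary outcomes, the ODI and the VAS, must be statistically significant at an overall two-sided" 0.05 level), and so does the SAP Summary ("Both of the co-primary endpoints need to meet statistical significance for the" trial to succeed).

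After a significant overall test, all pairs are compared by the Dwass-Steel-Critchlow-Fligner (DSCF) method. SAP 13 explains that DSCF was added to "evaluate which comparisons are significantly" different. Nothing makes a DSCF result a condition of success.

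The protocol does not fill the gap. Its synopsis states a three-group null of no difference, and Section 6 describes the comparison as allograft against conservative care. SAP 4 sizes the trial for a two-group rank-sum test: "A sample size of 40 in each group will have 80 % power to detect" the assumed difference.

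**The concern.** The stated objective is the efficacy of allograft, but the rule answers a different question: whether the three arms are all alike. Its type I error is controlled for that global null and not for the null that allograft is no better than saline.

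The gap matters in this design. Under Protocol 6.3, conservative-care subjects know their assignment, while the two injected arms do not know which product they received. ODI and VASPI are self-rated. A response to receiving any injection could separate conservative care from both injected arms, and the rule would count that as a successful allograft trial. It could also be met with ODI and VASPI differing through different pairs of arms, or with allograft the worst arm.

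**Working it through.** **Inputs from the documents.** Arms 140/40/40, SD 15.5, difference 9 points, minimum clinically important difference 6 points, two-sided 0.05 (SAP 4). Tests and rule from SAP 9.1.

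**Assumptions, because the documents give no figure.** Normal changes; VASPI with the same standardised effect as ODI; ODI-VASPI correlation 0 to 0.7 (0 to 0.8 where marked); no dropout.

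**The plan's own figure.**
- P(x<y) = Φ(−9/(15.5·√2)) = 0.341, as stated.
- Noether power, 40 v 40, two-sided: Φ(√(12·80·0.25)·0.159 − 1.960) = Φ(0.503) = 69%. Simulation gives 70%.
- One-sided 0.05: Φ(2.463 − 1.645) = 79%. Only this version comes near the stated 80%.
- 140 v 40, two-sided: Φ(√(12·180·(140/180)·(40/180))·0.159 − 1.960) = 87%.

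The shortfall is a separate matter. What counts here is that the calculation is for two groups on one endpoint, not for the three-group tests that decide success.

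**Simulation.** 20,000 trials per setting (10,000 in rows marked *). Kruskal-Wallis is referred to chi-square with 2 df. The DSCF cut is the 95% point of the studentized range for three groups divided by √2, which is 2.344. No crossover in this table.

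| True state | Rule as written | Plus DSCF allograft better than saline, both endpoints |
|---|---|---|
| Allograft = saline, conservative care 9 worse | 69-74% | at most 0.2% |
| Same, 6 worse* (corr. 0-0.8) | 22-36% | at most 0.3% |
| Same, 12 worse* (corr. 0-0.8) | 95-96% | at most 0.4% |
| ODI 9 worse only in conservative care, VASPI 9 worse only in saline | 67-69% | about 1% |
| Allograft 9 worse than both arms* (corr. 0-0.8) | 92-94% | 0% |
| Allograft 9 better than both arms | 92-93% | 61-69% |
| All three equal* (corr. 0-0.8) | 0.2-2.0% | at most 0.2% |

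**Crossover.** Protocol 7.1.4 lets conservative-care subjects cross to allograft after month 3 with a new Day 0 and baseline. The documents give no rate, and the SAP does not say which 12-month change such a subject contributes. In the primary population, "Subjects are analyzed under the treatment to which they were randomized", so crossovers dilute the conservative-care deficit. If crossing is unselected, a 9-point deficit becomes 0.75·9 = 6.75 points at 25% and 4.5 points at 50%. For allograft = saline and conservative care 9 worse, the rule as written is met as follows:
- 25% cross, unselected: 31-42%.
- 25% cross, the worst at 3 months, then like any allograft subject (3-to-12-month correlation 0.5-0.7, assumed): 11-19%.
- 25% cross, the worst at 3 months, gaining 9 points and keeping their own deviation: 34-49%.
- 50% cross: 7-16% unselected, 1-3% if the worst cross and then do like allograft subjects.

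**Which pair closes the gap.** Requiring a DSCF win over conservative care alone still gives success in 60-67% of trials when allograft equals saline (9-point case, no crossover). Requiring a win over saline on both endpoints limits it at any correlation: joint success cannot exceed the chance that one endpoint passes, 1 − Φ(2.344) = 0.95%. Simulation at correlation 1 gives 0.9%.

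**The case against.** Five points can be made for the plan.

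1. The SAP says both endpoints need to be significant, which read literally is a necessary condition only. But no other criterion appears anywhere, so on that reading success is undefined and the same edit is needed.
2. DSCF comparisons are mandatory after a significant test, so a null allograft-saline result would be printed beside the verdict. This is true and limits the harm: the risk is a wrong verdict, not a hidden result. It does not change what the rule declares.
3. Saline is not the comparator named in Protocol Section 6, and its blinding is partial: site staff know assignments and may assist with the questionnaires. The choice does need the sponsor's justification. Saline is still the only contrast in which subjects are blinded, and a win over conservative care alone leaves the flaw in place.
4. The 69-74% needs a full 9-point deficit on both scales and no crossover. This stands as a caution about size. Crossover is expected by design, and the 6-point case is much lower.
5. The different-pairs case is unlikely for two related self-reported scales. It shows what the rule permits and is not a forecast.

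**Conclusion.** The concern holds. As written, the rule can declare an allograft success when allograft equals saline, or even when it is worse. That follows from the wording and needs no numerical assumption.

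The size is illustrative. It rests on normal data, a VASPI effect mirroring ODI, the stated range of endpoint correlation and no dropout, and crossover moves it most. Because the rule decides the trial's main conclusion, it must be corrected.

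**What to change.** In SAP 9.1, SAP 7.5 and the Summary, state that success requires, on both ODI and VASPI change at 12 months, a significant Kruskal-Wallis test and a significant DSCF allograft-versus-saline comparison in favour of allograft. This uses only tests already planned and keeps the stated family-wise control. Give the reason for choosing saline, and state its limit (unblinded staff who may help with questionnaires).

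In the protocol, keep the three-group null as the first step. Amend Section 6 to say that saline decides success and that conservative care is reported through its own DSCF pair.

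Record the change in SAP 13 before database lock, with the date and the blinding status of those deciding. This is needed because SAP 13 already describes imaging as collected ("Therefore, there is no x-ray data to analyze"), site staff know assignments, and subjects are unblinded at exit or on consent to the extension.

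No new data are needed. The cost is power when allograft is truly 9 points better than both arms:
- No crossover: 92-93% falls to 61-69%.
- Worst 25% cross over: 73-76% falls to 60-68%.
- Worst 50% cross over: 65-73% falls to 59-68%.

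If the sponsor cannot accept that, the fallback is one pre-specified unadjusted two-sided 0.05 rank-sum test of allograft against saline on each endpoint, with allograft against conservative care next in fixed sequence. It gives 77-82% in all three cases and is closer to the two-group basis of SAP 4, but DSCF would no longer be the deciding test. Success when allograft equals saline on both endpoints would then be at most 0.8% at correlation up to 0.7, and about 2.5% at any correlation.
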